7.2 Sample Size Estimates

Assumptions:

- The sample size estimation is based on the results reported in the placebo arm of the Adaptive COVID-19 Treatment Trial (NCT04280705)
- On day 15, 61% of subjects in NCT04280705 placebo group remained hospitalized.
- The odds ratio of improvement in the ordinal scale in the Proxalutamide arm compared to the Proxalutamide placebo is at least 2.0
- The study has two arms with randomization at 1:1 ratio
- 90% power to detect an odds ratio of 2.0 using a two-tailed test with a type I error rate of 5%
- According to NCT04280705 protocol “The sample size to detect a given odds ratio for 1:1 randomization using a 2-tailed test at level α is estimated by the equation below. λ is the log odds ratio, p_i is the overall probability (combined over both arms) of being in the i th category of the K ordinal outcomes, and $z_{\alpha/2}$ and z_{β} are the $1 - \alpha/2$ and $1 - \beta$ quantiles of the standard normal distribution.”

$$\frac{12(z_{\alpha/2} + z_{\beta})^2}{\lambda^2(1 - \sum_{i=1}^K p_i^3)}$$

- The estimated distribution is based on NCT04280705 protocol scenario 4
- 3.5% of the subjects will not complete the study based on NCT04280705

Sample Size Estimate:

CONFIDENTIAL

This material is the property of the Applied Biology Inc. Do not disclose or use except as authorized.

Based on the assumptions above, we calculated that at a minimum we would need to recruit for each cohort 294 subjects (147 subjects in each arm) i.e., a total of approximately 600 subjects.

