
No measure of effect
	
Included measure of effect: Overall Recovery Ratio [time frame: 14 days]
	
Although we meant to calculate the overall recovery ratio, the outcome was not clearly described in the statistical plan of the protocol, and sample size was based on odds ratio for recovery.

6. Sample size calculation

As proposed in the final protocol	Done in the final statistical Plan	Rationale

The sample size estimation is based on the results reported in the placebo arm of the Adaptive COVID-19 Treatment Trial (NCT04280705) protocol scenario 4: On day 15, 61% of subjects in NCT04280705 placebo group remained hospitalized. For 90% power to detect an odds ratio of 2.0 using a two-tailed test with a type I error rate of 5%, and 3.5% of the subjects will not complete the study based on NCT04280705
	
No change.
 
However, we noticed that the way the sample size estimation was described may be hard for many readers to follow it.
 
An odds ratio for improvement of 2 over a baseline recovery risk of 39% (NCT04280705, scenario 4), results in a difference of 14% in the absolute recovery rate. The sample size was calculated to be able to detect a difference of 14% in Overall Recovery Rate at 14 days (risk ratio of 1.36) with a power of 90% and a type I error of 5%, over the estimated 39% recovery rate for the placebo group, and 3.5% non-compliance/cross over in the study groups.
	
Although no change was done in the sample size estimate, we rewrote it using simpler and more direct terms.

Sample size estimate: Based on the assumptions above, we calculated that at a minimum we would need to recruit for each cohort 294 subjects (147 subjects in each arm) i.e., a total of approximately 600 subjects.
	
No change
	
We verified that the sample size was still 90% powered after inclusion of baseline score 6 to the final protocol.

These minor changes in the statistical analysis plan were performed while writing the manuscript.

Researchers involved in the statistical analysis that implemented the changes:

[name], MD, PhD

[name], DDS, PhD

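### The final plan turns an odds ratio of 2 on 39% recovery into 14 points when it is 17.1, and the 90% binary power it states does not hold at the 294 per cohort it keeps, only for both cohorts pooled

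*Combined protocol and SAP*

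**What the plan says.** Protocol section 7.2 (the version with male and female cohorts) takes 61% of placebo patients as still hospitalised at day 15. It asks for "90% power to detect an odds ratio of 2.0 using a two-tailed test with a type I error rate of 5" per cent, uses a proportional-odds formula for the full ordinal scale, allows that "3.5% of the subjects will not complete the study based on NCT04280705", and concludes that the trial must "recruit for each cohort 294 subjects (147 subjects in each arm) i.e., a total of approximately 600 subjects".

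The final statistical plan makes the primary efficacy measure a binary one, recovery at day 14 (ordinal scores 1 and 2), tested by chi-square (sections 1, 4 and 5). Its section 6 marks the sample size as unchanged but restates its basis:

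- "An odds ratio for improvement of 2 over a baseline recovery risk of 39% (NCT04280705, scenario 4), results in a difference of 14" per cent.
- The size was calculated to "detect a difference of 14% in Overall Recovery Rate at 14 days (risk ratio of 1.36) with a power of 90" per cent, over 39% recovery on placebo, with "3.5% non-compliance/cross over in the study groups".
- On the rewriting: "Although no change was done in the sample size estimate, we rewrote it using simpler and more direct terms".
- On the size: "We verified that the sample size was still 90% powered after inclusion of baseline score 6 to the final protocol".

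**The concern.** Two statements in section 6 can be checked from the plan's own inputs, and both fail as written.

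First, the stated difference and risk ratio do not follow from the stated odds ratio. A reader cannot tell whether the design effect is an odds ratio of 2 or the smaller effect that 14 points represents.

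Second, the size printed beside the 90% claim is the per-cohort size. It came from an ordinal formula for an odds ratio of 2, and it is now said to have been calculated for a 14-point difference in a binary rate. The effect measure, the test and the size of the effect have all changed, so this is more than a restatement in simpler terms. The plan reports results by gender with confidence intervals, and the protocol sized each sex separately. A reader could therefore take the 90% to describe each cohort, where it does not hold.

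**Working it through.** **Inputs.** Placebo recovery 39% (100% minus 61%, protocol 7.2; stated as 39% in final plan section 6). Odds ratio 2, two-sided 5%, 1:1 allocation, 147 per arm per cohort, 3.5% allowance (both documents). Stated effect: 14 points, risk ratio 1.36 (final plan section 6).

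**1. Conversion.**

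- Placebo odds = 0.39/0.61 = 0.6393. Doubled = 1.2787. Probability = 1.2787/2.2787 = 0.5612.
- Difference = 0.5612 − 0.39 = 0.171. Risk ratio = 0.5612/0.39 = 1.44.
- The plan's figures run 39% to 53%: risk ratio 0.53/0.39 = 1.36, as stated, but odds ratio (0.53/0.47)/(0.39/0.61) = 1.76.

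Other readings do not give 14 points either:

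| Reading | Difference |
|---|---|
| 39% as the average of the two arms, odds ratio 2 (30.85% vs 47.15%) | 16.3 points |
| 3.5% switching in each arm: 17.1 × (1 − 0.07) | 15.9 points |
| Odds ratio 2 in the wrong direction (39% down to 24.2%) | 14.8 points |

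**2. Power of the chi-square test.** With p0 and p1 the recovery rates, p̄ their mean and n per arm:

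power = Φ{ [ |p1 − p0| − 1.96 √(2p̄(1−p̄)/n) ] / √[(p0(1−p0) + p1(1−p1))/n] }

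For 14 points at n = 147: [0.14 − 1.96 × 0.05813]/0.05756 = 0.453, and Φ = 67.5%.

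For an odds ratio of 2 at n = 147: [0.1712 − 1.96 × 0.05825]/0.05739 = 0.993, and Φ = 84.0%.

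For 14 points with both cohorts pooled, n = 294: [0.14 − 1.96 × 0.04111]/0.04070 = 1.460, and Φ = 92.8%.

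| | 14 points (39% vs 53%) | Odds ratio 2 (39% vs 56.1%) |
|---|---|---|
| One cohort, 147 per arm | 67.5% | 84.0% |
| One cohort after 3.5% loss, 142 per arm | 65.9% | 82.7% |
| Pooled, 294 per arm | 92.8% | 98.7% |
| Pooled after 3.5% loss, 284 per arm | 91.9% | 98.4% |
| Pooled, 294 per arm, 3.5% switching in both arms | 88.8% | 97.3% |
| Pooled, 294 per arm, 3.5% in the active arm only | 91.0% | 98.1% |

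The switching rows move each affected arm's rate 3.5% of the way towards the other arm's. For 14 points that is 39.49% vs 52.51% with both arms affected, and 39% vs 52.51% with the active arm only.

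Exact enumeration of the uncorrected chi-square test at 147 per arm gives 68.6% and 84.8%, so the normal approximation is not the cause of the gap. A power of 90% needs 265 per arm for 14 points or 177 per arm for an odds ratio of 2 (275 and 184 after dividing by 0.965).

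**3. The ordinal 294.** The formula in protocol 7.2 gives 12(1.960 + 1.282)²/(ln 2)² = 262.4, divided by (1 − Σp³). After division by 0.965 this is 294 if Σp³ is 0.075, which is possible on an eight-category scale. The category probabilities of scenario 4 are not printed, so the ordinal 294 can be neither confirmed nor refuted.

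**The case against.** The best answer is that the 67.5% belongs to no test in the plan. The final plan's primary measure is the overall 14-day recovery ratio, and its null hypothesis (section 4) concerns hospitalised patients with COVID-19, not one sex. Gender is listed in section 2 among subgroups for which no hypothesis test was done. Sizing and randomising within each cohort does not create a per-cohort test. This stands. A reader might infer that the primary test is underpowered; the documents do not support that, because on about 588 to 600 patients its power for 14 points is close to the stated 90% and for an odds ratio of 2 is well above it.

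It can also be said that 14 points is smaller than an odds ratio of 2 implies, so planning on it is cautious for the pooled test, and that the rewriting happened during manuscript preparation, so no recruitment decision hung on it. Both are fair, and they limit the consequence. They do not make the stated conversion correct, nor the 90% true at the per-cohort size beside it.

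A reader might also infer that the claim of still having 90% power is false. The plan does not say which calculation was checked. It may have been the ordinal one: the size is marked unchanged and section 4 says the distribution is still tested. The sentence is unspecified, not refuted.

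Finally, 88.8% should not be presented as the pooled power. It assumes 3.5% switching in both arms. Non-compliance in the active arm alone, or 1.75% in each arm, gives 91.0%.

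**Conclusion.** The concern holds as an error in stated figures. An odds ratio of 2 on 39% is 17.1 points and a risk ratio of 1.44, not 14 points and 1.36; the stated difference is an odds ratio of 1.76. The 90% binary power does not hold at 147 per arm: it is about 66% to 68% for 14 points and 83% to 84% for an odds ratio of 2. It holds approximately for the comparison of both cohorts together.

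This rests on a two-sided 5% uncorrected chi-square test, 39% recovery on placebo in both sexes, the planned numbers, and reading the overall recovery ratio as one unstratified comparison of men and women together. What fails is the stated basis of the sample size, not the adequacy of the primary test.

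**What to change.** Wording only, in section 6 of the final statistical plan:

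- State that an odds ratio of 2 on 39% gives 56.1%, 17.1 points and a risk ratio of 1.44. If 14 points is the intended target, state an odds ratio of 1.76 instead.
- Say that the 90% binary power for 14 points refers to the pooled comparison of about 588 to 600 patients, and give per-cohort binary power as about 66% to 68% (14 points) or 83% to 84% (odds ratio 2).
- Say which calculation was verified after baseline score 6 was added: ordinal or binary, per cohort or pooled.
- Say whether the 3.5% is loss, as in protocol 7.2, or non-compliance and cross-over, as in section 6, and in which arms.

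As a separate minor point, protocol section 7.5 still ends the study at completion by 294 subjects without saying whether that is per cohort; reconcile it with 7.2.

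The cost is a few sentences. No patients and no new analysis are needed; the stated per-cohort binary power becomes less favourable.

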6.4.3 Reporting Unanticipated Problems to Subjects

Subjects will be informed of any UPs that occur as part of their participation in this trial.

7 Statistical Plan

7.1 *Statistical Methods*

I. General Principles:

- Double-blinded, placebo controlled randomized interventional study with a two-sided type I error rate of 0.05.
- Continuous variables will be expressed as median (interquartile range [IQR]) and categorical variables will be expressed as a number
- 95% confidence intervals will be calculated for the primary outcome
- Group comparisons will be analyzed by the Wilcoxon rank sum test or χ^2 test
- The placebo arm will be used as a reference group when calculating treatment effects
- Differences between rates of clinical improvement will be calculated using unadjusted ordinal logistic regression or Cox proportional hazard models
- Statistical analyses will be conducted using XLSTAT version 2020.5.1 (Addinsoft, Inc.)

II. Statistical Hypotheses:

The primary endpoint is the distribution of clinical assessments on the COVID-19 ordinal scale at day 14. The primary outcome will be analyzed using the Wilcoxon rank sum test.

The Null Hypothesis (H_0) is that the distribution of clinical assessments on the COVID-19 ordinal scale at day 14 among hospitalized COVID-19 subjects treated with Proxalutamide is equal to the distribution of clinical assessments on the COVID-19 ordinal scale at day 14 among hospitalized COVID-19 subjects treated with the Proxalutamide placebo

The Alternative Hypothesis (H_A) is that the distribution of clinical assessments on the COVID-19 ordinal scale at day 14 among hospitalized COVID-19 subjects treated with Proxalutamide is not equal to the distribution of clinical assessments on the COVID-19 ordinal scale at day 14 among hospitalized COVID-19 subjects treated with the Proxalutamide placebo

Mathematically written as:

$$H_0: P(X > Y) = P(Y > X)$$

$$H_A: P(X > Y) \neq P(Y > X)$$

Where X and Y are randomly selected clinical assessments from the two treatment arms in the study.

III. Primary Efficacy Analysis:

- The non-parametric Wilcoxon rank sum test (Mann Whitney U) will be used to assess the primary end point.
- P-values <0.05 will be considered significant. All statistical analysis will be based on the intent-to-treat (ITT) population. All missing data will be described.

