7.6 Accountability Procedure

The data will be analyzed by a bio-statistics expert. The data will also be independently verified by an outside expert consultant.

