7.7 Deviation Reporting

No deviation from the plan will be implemented without the prior review and approval of the EC/IRB.

8 Direct Access to Source Data/Documentation

The PI and hospital will permit trial-related monitoring, audits, IRB/IEC(s) review and regulatory inspection(s) by providing direct access to source data/documentation.

9 Quality Control and Quality Assurance

Every effort will be made to keep staff assignments consistent throughout the entire study. The PI who assesses the subject at baseline should follow the subject throughout the completion of the study. This will ensure that this study is conducted – and that data is generated, documented (recorded), and reported - in compliance with this protocol, with GCP, and any other applicable regulatory requirements. The study monitor will audit the study procedures and CRFs throughout the study.

10 Ethical Considerations

This study will be conducted according to US and international standards of Good Clinical Practice (FDA regulations 21 CFR 312 for IND studies and FDA guidance E6) for all studies. Applicable government regulations and hospital research policies and procedures will also be followed.

This protocol and any amendments will be submitted to the Institutional Review Board (IRB) for formal approval to conduct the study. The decision of the IRB concerning the conduct of the study will be made in writing to the investigator.

All subjects for this study will be provided a consent form describing this study and providing sufficient information for subjects to make an informed decision about their participation in this study. This consent form will be submitted with the protocol for review and approval by the IRB. The formal consent of a subject, using the IRB-approved consent form, will be obtained before that subject is submitted to any study procedure. This consent form must be signed by the subject or legally acceptable surrogate, and the investigator-designated research professional obtaining the consent.

11 Data Handling and Record Keeping

During enrollment, each subject will be assigned a number. The numbers will be consecutive starting at 001.

During enrollment a record will be created for each subject. Each record will contain the subject's demographics, subject's efficacy parameters and any adverse events or study related information.

The subjects' records will be stored and handled in the same manner as the PI's patients' records.

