Revision	Description of Change		Date	Signature
1	New draft release	[name]	Dec 27, 2020	
2	Amendments to end points	[name]	Dec 29, 2020	
3	Amended AE section	[name]	Dec 30, 2020	
4	Amended to include female cohort	[name]	Jan 10, 2021	
5	Final review for female cohort	[name]	Jan 10, 2021	
6	Added exclusions for sexual activity and minor corrections	[name]	Jan 11, 2021	
7	Changed randomization model	[name]	Jan 19, 2021	
8	Amended inclusion criteria	[name]	February 1, 2021	

CONFIDENTIAL

This material is the property of the Applied Biology Inc. Do not disclose or use except as authorized.

FINAL STATISTICAL PLAN WITH SUMMARY OF CHANGES FROM THE FINAL PROTOCOL

We had to make minor adjustments to the statistical plan of the final protocol while writing the manuscript to make the statistical plan more stringent and clearer. The rationale for each change or no change is also presented.

Table of contents:

1. Primary Outcome Measure.....	1
2. Secondary Outcome Measures	2
3. General principles.....	4
4. Statistical hypothesis	5
5. Primary analysis efficacy.....	6
6. Sample size calculation	7

1. Primary Outcome Measure

Proposed in the final protocol	Final statistical Plan	Rationale
Treatment efficacy of proxalutamide relative to placebo arm as assessed by the COVID-19 ordinal scale [time frame: day 14]	No change	The distribution analysis of all the COVID-19 8-point ordinal scale scores at day 14 covers all possible scores, 1 to 8. This is better illustrated graphically for group comparison.
No specific measure of effect was appointed for the Primary efficacy analysis (quantitative efficacy measure).	Recovery ratio was defined as the measure of effect for the primary outcome. The treatment efficacy of proxalutamide was assessed by the proportion of recovered patients in both study arms [time frame: 14 days]. Recovery was defined as reaching scores 1 and 2 in the COVID-19 ordinal scale	Scores 1-2 represent a clear cut for recovery (alive hospital discharge).

2. Secondary Outcome Measures

As proposed in the final protocol	Done in the final statistical Plan	Rationale

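### The primary endpoint, test and hypotheses were replaced while the manuscript was being written, with no EC/IRB approval recorded, yet the changes are called minor and partly presented as the original plan

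*Combined protocol and SAP*

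**What the plan says.** Protocol 7.1 (Primary Efficacy Analysis) is explicit: "The non-parametric Wilcoxon rank sum test (Mann Whitney U) will be used to assess the primary end point". Both hypotheses there concern the distribution of the Day-14 scores. Protocol 7.7 states: "No deviation from the plan will be implemented without the prior review and approval of the EC/IRB". Protocol 7.6 adds an independent check: "The data will also be independently verified by an outside expert consultant".

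The appended document is titled "FINAL STATISTICAL PLAN WITH SUMMARY OF CHANGES FROM THE FINAL PROTOCOL". It opens with "We had to make minor adjustments to the statistical plan of the final protocol while writing the manuscript" and closes with "These minor changes in the statistical analysis plan were performed while writing the manuscript". Its last line introduces those responsible as "Researchers involved in the statistical analysis that implemented the changes". It sets protocol text, changed text and rationale side by side in six tables. The protocol's revision history ends at revision 8 (February 1, 2021), described as "Amended inclusion criteria".

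**The concern.** A confirmatory p-value keeps its stated 5% error rate only if the endpoint, test and hypotheses were fixed without knowledge of the results. Here all three were replaced at manuscript stage by the people doing the analysis, and at least one other change cites findings. The trial's own safeguard against this is prior EC/IRB approval, and nothing shows that it was used.

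The table discloses the changes, but its wording blurs their status. If readers take the right-hand column as the plan, they will read an analysis chosen late as the one the trial was designed to test.

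**Working it through.** **1. Protocol (7.1, 7.3, 3.1) against the final statistical plan**

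- *Primary endpoint and test.* Protocol: the Day-14 distribution, by Wilcoxon. Final plan, sections 4 and 5: a recovery ratio from dichotomising at scores 1-2, by chi-square, with Wilcoxon called unsuitable for the new variable.
- *Hypotheses.* Protocol: equality of distributions. Final plan: both rewritten as association between treatment and recovery.
- *Secondary outcomes.* Duration of new oxygen use and Day-14 PCR positivity are excluded, on grounds of poor site reporting and lack of funds.
- *Subgroups.* Protocol: age and androgen status. Final plan: baseline score, gender and hospital site. The age rationale says that lower cut-offs gave nothing relevant to report, so findings had been seen.
- *Models.* Ordinal logistic regression is dropped, and Cox regression is kept only for death.

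**2. Statements that give the new analysis the standing of the plan**

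- The opening and closing both call the changes minor.
- Section 3 says the primary hypothesis testing was kept, while sections 4 and 5 replace it.
- Section 5 says that the recovery ratio had been intended all along.
- The first sample-size row is marked as unchanged but is restated on the binary endpoint, with figures that do not follow. Odds at 39% are 0.39/0.61 = 0.639. Doubled, they are 1.279, and 1.279/2.279 = 56.1%. That is a difference of 17.1 points, not the 14 stated.

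**3. Status of the protocol test.** Section 4 says the distribution is still tested for significance. Section 5 says Wilcoxon was used for some of the secondary outcomes. The two do not settle whether the Day-14 Wilcoxon test was run, or with what status.

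**4. Approval.** None of the eight logged revisions covers these changes, and the final plan mentions no EC/IRB review.

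**5. Size of the error-rate effect**

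Inputs:
- two-sided alpha 0.05 (7.1);
- 147 per arm for one cohort (7.2), or 2 × 147 = 294 per arm for both;
- recovery cut-offs at scores 1-2 (3.1) and 1-3 (5.1, Time to Recovery);
- category probabilities p_i, which the documents do not give and which are therefore assumed, with 39 to 45% at scores 1-2. The lower value is 100 − 61 from 7.2.

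Under the null, the Wilcoxon and cut-off statistics are approximately bivariate normal. With π the proportion at or below the cut-off, their correlation is ρ = √[3π(1−π)/(1−Σp_i³)]. The chance that at least one is significant is 1 − P(|Z_W|<1.96 and |Z_C|<1.96).

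Worked example, with assumed probabilities for scores 1 to 8 of 0.10, 0.29, 0.03, 0.10, 0.20, 0.12, 0.08, 0.08:
- Σp_i³ = 0.0372
- ρ = √(3 × 0.39 × 0.61/0.9628) = √0.741 = 0.861
- either test significant: about 7.4%
- with the 1-3 cut-off added: about 8.4%

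Finite-sample simulation (20,000 null trials per setting, four assumed distributions, 147 or 294 per arm, tie-corrected Wilcoxon):
- each test alone: about 5%, the plan's own figure
- Wilcoxon or scores 1-2: 7.1 to 7.5%
- Wilcoxon, scores 1-2 or scores 1-3: 8.1 to 9.0%

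The three-test figure rises with the share at score 3. An assumed 12% there gave up to 9.5% at 147 per arm.

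**The case against.** The best defence is openness: the document's title announces a summary of changes, every change has a rationale, and the timing is stated twice. That stands. A reader might infer that the manuscript passes the new analysis off as planned, but the manuscript is not among the documents and the table points the other way. What remains is the wording that blurs status.

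A reader might also infer a proven breach of 7.7. The documents support only that no approval is recorded. Approval correspondence need not appear in either document.

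Counting rows suggests wholesale rewriting: 17 of the 20 table rows are not marked as unchanged. The count is correct but a poor measure. About six rows describe the single move to a binary endpoint, and others concern naming, percentages, extra intervals or software.

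A free choice among the Wilcoxon test and all seven possible cut-offs would give about 20 to 21% false positives. That does not describe this trial. Scores 1-2 already defined recovery in 3.1 and scores 1-3 in 5.1, so the protocol names two cut-offs.

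Finally, only the age rationale clearly cites results. The oxygen and PCR exclusions cite reporting and funding, and the proportional-hazards remark describes what was done, not why.

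**Conclusion.** The point holds in this form. The primary endpoint, test and hypotheses, two secondary outcomes, the subgroups and the ordinal model were changed at manuscript stage by the analysts, without recorded approval and, for the age subgroup, after findings had been seen. The label of minor changes is not justified, and the statement that primary testing was kept is contradicted in the same document.

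The measurable effect on the primary claim is modest: about 7 to 7.5%, or about 8 to 9% with the second recovery cut-off, against 5%. These figures assume that significance on any of the tests would have been accepted as success, and they rest on assumed category distributions. They do not show that the cut-off was picked for its result. The documents do not establish that outcome data had been seen when the primary analysis was changed, which is why the plan should say so. Recorded approval would settle the 7.7 question but would not make the changes prespecified.

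**What to change.** - Report the Day-14 Wilcoxon test as the primary confirmatory result, and the other analyses in protocol 7.1 to 7.3 wherever the data exist. Reconcile sections 4 and 5 of the final plan on whether that test was run.
- Label the recovery-ratio primary analysis, the replacement subgroups and the other substantive changes as post hoc, in the plan and in the results tables. Software, percentages and added intervals need no such label.
- Delete the description of the changes as minor and the statement that primary testing was kept. State for each change whether outcome data had been seen.
- Cite the EC/IRB approval if one exists. If not, report the changes to the EC/IRB as deviations made without prior approval. A later submission cannot satisfy a rule that requires approval beforehand.
- Have the outside consultant provided for in 7.6 verify the protocol analyses.

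The cost is relabelling, one EC/IRB communication and analyses already specified, with no new data. The downside is that the headline claims may become more cautious.
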